## 3. Outcomes

### *3.1 Primary outcome*

Patient utility surveys will use a 5-point Likert scale for responses scored 1-5. The two co-primary outcomes will compare the scores for the following two questions, **measured at 6 months (or 3 months if the patient did not complete their 6 month survey)**, between **intervention patients** (Arms B + C) and **control patients** (Arm A).

- How well do you feel your oncology team understands your symptoms (e.g. nausea, vomiting, weight loss, etc.)?
- How well do you feel your oncology team understands your activity level and ability to function?

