### *3.2 Secondary outcomes*

The following secondary outcome will compare the same questions:

- **Measured at 3 months**, between **intervention patients** (Arms B + C) and **control patients** (Arm A).

We will compare cumulative adherence for patients in the intervention group (arm B and arm C). Each week, adherence will be defined as each week where the patient submits the weekly survey (i.e. adherence to PRO) and has step data for 4 of 7 days of the week (i.e. adherence to Fitbit platform), divided by the total number of weeks that the patient is enrolled in the trial.

- Comparison of mean patient adherence at three months for patients in arm B vs arm C
- Comparison of mean patient adherence at six months for patients in arm B vs arm C

We will analyze trends in the PROStep data (PRO surveys and Fitbit step data).

- Comparison of PRO scores between patients in arm B vs. arm C. These will be measured using mean and median composite symptom scores as reported by patients in their PRO surveys. The composite score is the sum of the scores for each domain in the PRO survey, and the mean or median composite symptom score is the mean or median of all composite scores collected during the study.
- Fitbit step data will be measured using mean daily step counts for all days in which Fitbit data is collected. Days where the patient does not have Fitbit data will be excluded from these calculations.

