### 3.3 Exploratory outcomes

- The following exploratory outcomes will make the following comparisons for responses to the two questions in the primary outcomes:
  - Measured at 6 months (or 3 months if the patient did not complete their 6 month survey)
    - Between Arm B and Arm A
    - Between Arm C and Arm A
    - Between all Arms.
  - Measured at 3 months:
    - Between Arm B and Arm A
    - Between Arm C and Arm A
    - Between all Arms.
- Number of palliative care consults
- Number of documented advanced care planning (ACP) notes
- Number of documented serious illness conversations (SIC)
- Correlation between step, heart rate, distance, pace, elevation and sleep data trends, patient reported outcomes, patient and clinician ECOG assessment, and patient hospitalization and survival

- We will report descriptive statistics for the remaining questions on the patient utility surveys (mean and standard deviation) followed by t-tests between each individual arm and between all intervention patients (Arms B + C) and control patients (Arm A). Patient utility surveys include the following (the intervention arms receiving additional questions):
  - How well do you feel that your oncology team has addressed your symptoms?
  - How well do you feel that your oncology team has addressed your activity level and ability to function?
  - I feel that the PROStep data prompted better communication with my oncology team about my symptoms. **(arm b and arm c)**
  - I feel that the PROStep data prompted better communication with my oncology team about my activity level. **(arm b and arm c)**
  - My oncology team has discussed the PROStep data during my appointments. **(arm b and arm c)**
  - I feel that the PROStep data changed how my oncology team addressed my symptoms and/or ability to function. **(arm b and arm c)**
  - I feel that the PROStep data changed my oncology team's treatment of my cancer, such as decisions to start, continue, or stop cancer treatments like chemotherapy. **(arm b and arm c)**
  - I feel that the PROStep data triggered discussions with my oncology team about my prognosis or goals of my cancer care. **(arm b and arm c)**
  - I feel that regularly wearing my Fitbit is burdensome. **(arm b and arm c)**
  - I feel completing my weekly symptom surveys is burdensome. **(arm b and arm c)**
  - On a scale of 0-10, how likely is it that you would recommend PROStep to other patients with cancer? **(arm b and arm c)**

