## **9. Analysis plan**

For each primary outcome, we will compare the mean scores from the survey questions at 6 months (see section 3.1) for all 3 groups (2 intervention, 1 control) using a Kruskal-Wallis test with  $p < 0.05$  indicating statistical significance. If the result is significant, we will use the Tukey's honestly significantly difference (HSD) test to test pairwise comparisons. If the outcomes for any arm are skewed (not normally distributed), we will use log-transformation before applying all tests. For

clinicians who have completed a 3-month survey for a specific patient, but do not complete a 6-month survey for that patient, we will apply their 3-month survey responses in place of their missing 6-month survey for analysis for that specific patient. For example, if Clinician A completes a 3-month survey for Patient A, but not a 6-month survey, we will use the results from their completed 3-month survey in its place for Patient A (but not for other patients). That said, we will do a sensitivity analysis only using the coded 6 month analyses (complete case analysis).

We will repeat this analysis for the secondary outcome of composite survey score at 3 months. For patients who exit the study early, we will attempt to administer their next survey and use that assessment. These will be administered if patients have been enrolled for a minimum of 4 weeks of the enrollment period leading up to their following survey. For example, if a patient disenrolls 4 weeks after receiving their 3-month utility survey, they will be eligible for their 6-month survey whereas a patient who dis-enrolls at 3 weeks will not). If a patient dies or is otherwise unable to complete a survey, they will be omitted from the analysis for the relevant outcome. For patients who disenroll from the trial for any reason (voluntary, death, etc.), but meet this 4 week threshold, their clinicians will receive a utility survey. To assess whether responses in 3-month to 6-month surveys differ across arms, we will run an analysis of covariance (ANCOVA) model with the baseline score and arms as covariates, and change of score as the dependent variable.

We will use descriptive statistics to compare the secondary outcomes of adherence rates between the two intervention groups and trends in PROstep data. We will use Kruskal-Wallis tests for continuous outcomes and chi-square tests for categorical variables to compare these outcomes between all arms at 3 and 6 months.

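### The co-primary outcomes compare pooled Arms B+C with Arm A, but the analysis plan only runs a three-arm Kruskal-Wallis test with Tukey pairs

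*Combined protocol and SAP*

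**What the plan says.** Section 3.1: "The two co-primary outcomes will compare the scores for the following two questions", and the comparison is "between intervention patients (Arms B + C) and control patients (Arm A"). The time point is 6 months, with the 3-month answer used if the 6-month survey is missing.

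Section 3.2 sets the same contrast for the secondary time point: "Measured at 3 months, between intervention patients (Arms B + C) and control patients (Arm A").

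Section 3.3 opens "The following exploratory outcomes will make the following comparisons for responses to the two questions in the primary outcomes", then lists B versus A, C versus A and all three arms together, at both time points.

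Section 9, on the co-primary questions: "we will compare the mean scores from the survey questions at 6 months (see section 3.1) for all 3 groups (2 intervention, 1 control"), by Kruskal-Wallis at p < 0.05, then Tukey's HSD on pairs of arms if significant. For 3 months it adds "We will repeat this analysis for the secondary outcome of composite survey score at 3 months".

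A pooled test is named in one place only. Section 3.3 plans "t-tests between each individual arm and between all intervention patients (Arms B + C) and control patients (Arm A"), but limits it to the utility-survey questions that are not co-primary.

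**The concern.** The outcome definition and the analysis describe different comparisons. Section 3.1 asks a two-group question. Section 9 answers a three-group one, which the protocol itself ranks as exploratory for the same two questions.

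Three things follow.

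- A significant primary test would not establish the stated primary comparison, because the three-arm test has no direction and also responds to a difference between B and C.
- The plan does not say what to conclude when the three-arm test is significant but no pair involving Arm A is.
- No pooled effect or confidence interval is specified for either co-primary question.

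With two inconsistent specifications in force, which one becomes the reported primary result could be decided after the data are seen.

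**Working it through.** **1. Is the pooled test given anywhere?**

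| Place | Comparison | Covers B+C vs A on the co-primary questions? |
|---|---|---|
| Section 9, primary test | A, B, C as three groups | No |
| Section 9, follow-on | Tukey pairs of single arms | No |
| Section 9, ANCOVA | Change of score, arms as covariates | No pooled contrast named |
| Section 9, last paragraph | Kruskal-Wallis or chi-square across arms | No |
| Section 3.3, t-tests | B+C vs A | Other survey questions only |

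**2. What the three-arm test measures.** There is no power calculation in the plan to reproduce; 125 patients at 1:1:1 is all that is given. With n per arm and arm means μ in SD units, the signal (noncentrality) of a three-group test splits into two parts:

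λ = (2n/3)·[(μB+μC)/2 − μA]² + (n/2)·(μB − μC)²

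The first part is the Section 3.1 contrast. The second is B versus C, which is not part of the primary outcome. With n = 42 and μA = 0:

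- B and C both +0.5: λ = 28 × 0.25 + 21 × 0 = 7.0, all from the primary contrast.
- B 0, C +0.5: λ = 28 × 0.0625 + 21 × 0.25 = 1.75 + 5.25 = 7.0, three quarters of it from B versus C.

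The three-arm test barely distinguishes these two situations.

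**3. Power by formula** (equal benefit d = 0.5 in B and C, SD 1, n = 125/3 = 41.7, two-sided 0.05):

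- Pooled: d·√(2n/3) = 0.5 × 5.27 = 2.64; Φ(2.64 − 1.96) = 0.75.
- Three-group F with 2 and 122 df: λ = 2.64² = 6.94; power 0.64.
- One Tukey pair: 0.5/√(2/41.7) = 2.28 against a critical value of 3.36/√2 = 2.37; power 0.47.

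With 75 completers the same three figures are 0.53, 0.42 and 0.27.

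**4. Simulation on 5-point scores.** Assumed: control percentages 3/7/20/40/30 for scores 1 to 5, cut from a normal latent variable; B and C shifted by the stated SD; 10,000 replicates; tie-corrected tests. Tukey is on log scores, since Section 9 log-transforms skewed outcomes.

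| Per arm | Shift B, C | Pooled rank-sum | Kruskal-Wallis | Kruskal-Wallis plus a Tukey pair with A |
|---|---|---|---|---|
| 42 | +0.5, +0.5 | 66% | 55% | 44% |
| 42 | +0.25, +0.5 | 43% | 44% | 31% |
| 42 | +0.3, +0.7 | 65% | 72% | 58% |
| 42 | 0, +0.5 | 22% | 55% | 28% |
| 42 | −0.35, +0.35 (extreme) | 4% | 75% | 31% |
| 30 | +0.5, +0.5 | 52% | 42% | 33% |
| 30 | 0, +0.5 | 16% | 40% | 18% |

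With no effect at 42 per arm, the pooled test rejects in 4.8% and Kruskal-Wallis in 5.0%, so both hold their level. In the (0, +0.5) case at 42 per arm, 36% of trials have a significant Kruskal-Wallis test and a non-significant pooled test. In that case 49% of significant Kruskal-Wallis results have no significant pair involving Arm A.

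**The case against.** The strongest reply is that the size depends on the assumptions and does not point one way.

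- **Log scale.** The assumed scores are left-skewed and logging makes that worse (skewness −0.82 raw, −1.92 logged), which weakens Tukey. On raw scores the last column rises to about 52% for (+0.5, +0.5), 65% for (+0.3, +0.7) and 34% for (0, +0.5), and the 49% falls to about 37%. This stands: the log clause sets no skewness criterion, so both figures should be read together.
- **Scenarios.** The −0.35/+0.35 case has no basis in the documents. In (+0.25, +0.5) the two tests have equal power, and when C does much better than B the three-arm test has more. This also stands. The figures show that the tests ask different questions, not that power is always lost.
- **Reporting.** The plan does not forbid a pooled estimate; it only fails to specify one.
- **3 months.** Section 9 refers to a composite survey score, whereas Section 3.2 compares the two single questions. Whether these are the same outcome is unclear, so the carry-over to 3 months is less certain than the mismatch at 6 months.
- **Feasibility study, and Section 9 cites Section 3.1.** The plan still names co-primary outcomes and a significance threshold. The sentence that cites Section 3.1 also says three groups, so the cross-reference does not resolve the conflict.

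None of this supplies the missing test.

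**Conclusion.** The concern holds, and it must be fixed before analysis. It rests on the text alone: Sections 3.1 to 3.3 consistently make B+C versus A primary and the three-arm and single-arm comparisons exploratory, while Section 9 does the reverse.

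The size is illustrative, because the documents give no effect size, score distribution, power or dropout. Under the assumed distribution, with 42 per arm, the three-arm test has about 11 points less power than the pooled test when both arms gain 0.5 SD (55% against 66%). It is significant about two and a half times as often when only C gains (55% against 22%), mostly on the strength of a B versus C difference. How often a significant three-arm result lacks a pair involving Arm A (37% to 49% in the latter case) depends on whether Tukey is run on raw or log scores.

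**What to change.** Have the investigators confirm that Section 3.1 is the intended primary comparison. Then, in Section 9:

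1. For each co-primary question, specify one two-sided Wilcoxon rank-sum test of Arms B+C versus Arm A. Report it with the difference in mean score and its 95% CI, and state that the rank test gives the p-value and the interval describes the size. A log transformation does not change ranks, so that clause is not needed for this test. A prespecified pooled t-test would also remove the mismatch; its power was within about a point of the rank-sum test under the same assumptions.
2. Move the three-arm Kruskal-Wallis and Tukey tests to the exploratory analyses, where Section 3.3 already lists those comparisons.
3. Make the same change for the 3-month secondary comparison, and replace the reference to a composite score with the two questions named through Section 3.2, or define the composite.

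This changes wording only and needs no new data. The price is lower sensitivity if only one intervention arm works (22% against 55% in the case above). The exploratory arm comparisons would still show that pattern.

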## 5. Study design

### 5.1 Design

[figure not shown]
This prospective cohort study will evaluate the effect of remotely collected PROs and step data derived from wearable Fitbit devices, and remotely presenting those data to clinicians and patients at each oncology visit. We will enroll patients who are diagnosed with incurable lung or gastrointestinal cancer who are receiving (or planning to receive) chemotherapy. Eligible patients can have in-person or virtual visits with their oncology clinician prior to chemotherapy, which is of particular importance as many visits are now being done via telemedicine. Patients will be randomized into one of three arms – a control (arm a), an intervention with no patient feedback (arm b), and an intervention with patient feedback (arm c) – at a 1:1:1 allocation (**Figure 1: Patient Arms**). All intervention patients will receive 1) weekly PRO surveys for five symptoms administered through the W2H text platform and 2) a Fitbit wearable device that can track patient step, distance, active minutes, sleep, and heart rate data. At each subsequent medical oncology visit (either in-person or via telemedicine), oncology clinicians will receive a PROStep Dashboard that reports the patient’s 1) trends in the home-based PROs and step data, 2) acute care utilization in the prior six months (Oncology Evaluation Unit, emergency department or inpatient admissions), and 3) whether the patient has a documented Serious Illness Conversation (a type of Advance Care Planning note that is standard practice at PCAM). Arm C will receive a brief text message feedback including an active nudge question on their upcoming appointment.

Arm B will not receive text feedback. Arm A will receive no PRO surveys, Fitbit device, or patient feedback (arm a) (**Figure 2: Intervention by Patient Arm**). Patients will be enrolled for a total of six months, unless they disenroll earlier, and evaluated on the outcomes described above.

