### *5.4 Accrual*

The study sample will be drawn from patients who receive their cancer care from a GI or lung oncologist at the University of Pennsylvania's Perelman Center for Advanced Medicine (PCAM). We aim to enroll 125 patients. We anticipate enrolling these 125 patients over 6 months at a rate of 4 patients per week, a small fraction of the number of eligible patients with in-person or telemedicine visits at PCAM each week. A summary of recruitment mechanisms is found in Section 6 (Subject recruitment).

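### After a significant Kruskal-Wallis test, Section 9 switches to Tukey HSD on means, which adjusts again for multiplicity the gate already controls with three arms and so costs some power for pairwise arm comparisons

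*Combined protocol and SAP*

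**What the plan says.** Section 9 tests each of the two primary questions "for all 3 groups (2 intervention, 1 control) using a Kruskal-Wallis test" at 0.05. Only if that result is significant does it go on to Tukey's "honestly significantly difference (HSD) test to test pairwise comparisons". A further rule reads: "If the outcomes for any arm are skewed (not normally distributed), we will use log-transformation before applying all tests". The same analysis is repeated at 3 months.

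The outcome is a single ordinal item. Section 3.1 states: "Patient utility surveys will use a 5-point Likert scale for responses scored 1-5". The same section makes the pooled intervention arms (B + C) against control (A) the primary contrast. Section 3.3 lists the single-arm comparisons on these two questions, such as "Between Arm B and Arm A", as exploratory. No section names a rank-based pairwise method or says how to report a significant overall test with no significant pair.

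**The concern.** The two steps do not test the same thing. Kruskal-Wallis compares ranks; Tukey HSD compares means, using a pooled variance and normal-theory cut-offs, on a five-level item with many ties. The steps can disagree for that reason alone.

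The second step also pays twice for multiplicity. Among three arms there are three pairwise hypotheses, and if any two of them hold together then all three arms are equal. That joint hypothesis is what the gate tests at 0.05. By the closed-testing principle, each pair can then be tested at 0.05 with family-wise error held at 5% for that question. Tukey HSD controls that error without any gate, so gate plus Tukey is stricter than it needs to be.

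At stake is power for B v A, C v A and B v C in a small trial, and the awkward result in which the arms are declared different but no pair can be named. With no rule for that case, its reporting would be settled after the data are seen.

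**Working it through.** The plan states no power, effect size or SD, so there is no figure of its own to reproduce.

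**Inputs from the documents.** Section 5.4: "We aim to enroll 125 patients". Section 5.1: "at a 1:1:1 allocation". Hence 125/3 = 41.7, taken as 41 per arm. The gate is at 0.05 with 2 df.

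**Assumptions (not in the documents).**
- Evaluable number: 41 per arm (no loss) or 30 per arm (1 - 30/41 = 27% loss).
- Control distribution on scores 1 to 5: either 3/7/25/40/25% (mean 3.77, SD 1.00) or 1.4/5.3/17.5/37.7/38.1% (mean 4.06, SD 0.94).
- Effects are shifts on a latent normal scale. A shift of 0.6 moves the observed mean by 4.27 - 3.77 = 0.50 points in the first distribution. In the second it moves it by 0.44 points, or 0.44/0.94 = 0.47 of the observed SD.

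**Step 1: the extra adjustment.** With 3 x 41 - 3 = 120 df, Tukey's critical |t| is q/√2 = 2.37 against 1.98 unadjusted. That is a two-sided level of about 0.019 per pair.

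**Step 2: power per true pair.** Simulation used 40,000 trials per case for control mean 3.77 and 4,000 for 4.06. The tie-corrected Kruskal-Wallis gate at 0.05 was followed by Tukey on raw scores or by Wilcoxon at 0.05.

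| Control mean; latent shift | n per arm | Pair | Gate + Tukey | Gate + Wilcoxon | Loss (points) |
|---|---|---|---|---|---|
| 3.77; B and C 0.6 | 41 | A v B | 55.5% | 62.5% | 7.0 |
| 3.77; B and C 0.6 | 30 | A v B | 40.1% | 47.0% | 6.9 |
| 3.77; C only 0.6 | 41 | A v C | 50.0% | 61.7% | 11.7 |
| 3.77; C only 0.6 | 30 | A v C | 35.5% | 46.5% | 11.0 |
| 3.77; B 0.3, C 0.6 | 30 | A v C | 36.7% | 42.1% | 5.4 |
| 4.06; B and C 0.5 | 41 | per pair | 36% | 43% | 7 |
| 4.06; C only 0.6 | 41 | A v C | 45% | 59% | 14 |

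In the first row, Tukey without the gate finds 57.7%. Most of the loss is therefore Tukey's own adjustment (62.5 - 57.7 = 4.8 points); the gate adds 57.7 - 55.5 = 2.2.

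**Step 3: significant overall test, no significant pair.** Share = [P(gate significant) - P(gate significant and at least one Tukey pair)] / P(gate significant). For control mean 3.77, C only 0.6, 30 per arm: (56.1 - 51.2)/56.1 = 8.7%. Over shifts of 0.5-0.6 the share is 5.2-7.7% at 41 per arm and 7.3-9.0% at 30; with control mean 4.06 it is about 7-11%. With gated Wilcoxon it was 0% in every case run.

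**Step 4: the log rule.** Ranks do not change under a log, so the gate is unaffected. Scores bunched at the high end are left-skewed, and a log worsens that. At 41 per arm, control mean 3.77, B and C shifted 0.6, power for A v B under Tukey falls from 55.5% to 50.8%, and the no-pair share is (71.6 - 62.8)/71.6 = 12.3%. With B 0.3 and C 0.6 the share is 18.0%; with control mean 4.06 it reaches about 22%.

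**Step 5: false pairs.** With no difference between arms, the chance of any false pair per question is 3.8% (gate + Tukey) against 5.0% (gate + Wilcoxon) at 41 per arm, and 3.7% against 4.8% at 30. With control mean 4.06 at 41 per arm, false B v C when both are shifted 0.5 is 1.2% against 4.9%, and false B v A when only C is shifted 0.6 is 3.0% against 4.9%.

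**The case against.** The strongest reply is that little of consequence is affected. Section 3.1 makes pooled B + C versus A the primary contrast, Section 3.3 calls the arm-level comparisons exploratory, and the abstract describes a feasibility study. A conservative follow-up on exploratory pairs is defensible, and an overall test without a significant pair is a known property of omnibus testing. This stands as a limit on importance. A reader might infer that the trial loses power for its primary contrast; the documents do not support that, because neither Kruskal-Wallis nor Tukey on pairs tests the pooled contrast. Still, Section 9 places the pairwise step inside the analysis of each primary outcome, so those results will be read.

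A reader might also infer that Tukey buys nothing. It does buy something: step 5 shows lower false-pair rates. What it buys is error below the nominal 5% per question. Control is per question only, because Section 9 sets 0.05 for each of the two questions. If the questions were independent, the chance of any false pair over both would be 1 - 0.962² = 7.5% with Tukey and 1 - 0.95² = 9.75% with gated Wilcoxon.

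Finally, the sizes rest on assumed distributions and shifts. That is so, but two distributions agree on direction and rough size. The 14-point loss needs an effect in C alone; when both arms shift equally, the loss is about 6-8 points.

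**Conclusion.** The point holds as an inexpensive improvement, not as a threat to the trial's validity. Section 9 follows a rank test with a test of means that adjusts again where, with three arms, no further adjustment is needed within a question. Under the stated assumptions, each true pair loses about 5-14 points of power. About 5-11% of significant overall tests have no significant pair, or about 12-22% if the log rule is applied. With a very large effect (latent shift 1.5 in C) the no-pair problem vanishes.

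It would be wrong to conclude that false positives are inflated, since the fault is conservative. It would equally be wrong to say that arm differences are missed outright: they are missed somewhat more often. The log rule does not repair the step. The pooled contrast of Section 3.1 needs its own test, which is a separate matter that this change does not settle.

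**What to change.** Replace the Tukey sentence in Section 9 with:

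> If the Kruskal-Wallis test for a question has p < 0.05, each pair of arms is compared by a two-sample Wilcoxon test at two-sided 0.05 (closed testing for three arms; family-wise error is controlled at 5% within each question).

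Report with each pair an estimate that matches the rank test, for example the probability of a higher score with its 95% CI. If a mean difference and CI are also shown, label them descriptive: a mean-based interval can disagree with the Wilcoxon result and would bring back the mismatch. Unadjusted pooled-variance t-tests after the gate are not a safe substitute: with C alone shifted by 1.5 at 41 per arm, they declared the equal pair A v B different in 8.8% of trials, against 4.9% for Wilcoxon.

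The cost is one sentence on testing and one on estimation, with no extra patients or data. The downside is small: the chance of any false pair per question rises from about 3.7% to the nominal 5%, but not above it.

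### Section 9 tests an undefined composite survey score at 3 months, where Section 3.2 promises the two primary questions separately, arms B + C against arm A

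*Combined protocol and SAP*

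**What the plan says.** Section 3.1 sets two co-primary outcomes: "The two co-primary outcomes will compare the scores for the following two questions". One question concerns the team's understanding of symptoms, the other its understanding of activity and function. The scale is given there too: "Patient utility surveys will use a 5-point Likert scale for responses scored 1-5". The comparison is arms B + C against arm A.

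Section 3.2 carries this to 3 months: "The following secondary outcome will compare the same questions", again B + C against A. It mentions no composite of these answers. Later in 3.2 a composite is defined, but for the weekly PRO symptom survey, as a sum over symptom domains, and for a comparison of arm B with arm C.

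Section 3.3 lists the other utility-survey questions as exploratory, with "the intervention arms receiving additional questions". They are to be described by mean and standard deviation and then compared by t-tests. Nothing says that they are added together.

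Section 9 describes a three-group Kruskal-Wallis test for each primary outcome, with Tukey pairwise tests if it is significant. It then says: "We will repeat this analysis for the secondary outcome of composite survey score at 3 months".

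**The concern.** The outcome section and the analysis section name different variables for the same outcome. Section 3.2 has two scores and so two results; Section 9 has one score and one result, and does not say how the score is built. An analyst working from Section 9 would have to choose which items enter and whether to sum or average them. Left open, that choice could be made after the answers have been seen.

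This is the first secondary outcome listed in 3.2 and the only one there that sets intervention against control; adherence and symptom scores are B against C. The two questions also ask about different things, symptoms and function, so an effect on one need not appear on the other. A further hazard is that the survey is longer in arms B and C, so some ways of forming a composite would not measure the same thing in every arm.

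**Working it through.** The plan gives no range, scoring rule, effect size or power figure for this composite, so there is no stated figure to reproduce. The check is to see what the term could mean and what each meaning implies.

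**Item count (Sections 3.1 and 3.3)**
- Asked of all arms: 2 primary questions + 2 on whether symptoms and function were addressed = 4, scored 1-5.
- Asked of arms B and C only: 9. Eight are statements taken as scored 1-5, including two where agreement is unfavourable (for example "I feel that regularly wearing my Fitbit is burdensome"). One is on another scale: "On a scale of 0-10, how likely is it that you would recommend PROStep to other patients with cancer".
- Totals: arm A 4; arms B and C 4 + 9 = 13, of which 12 are on 1-5.

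**Reading 1: the only composite the text defines (weekly PRO symptom sum).** Section 5.1 gives arm A no PRO surveys. The score does not exist in arm A, so neither B + C versus A nor the three-group test can be run.

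**Reading 2: all utility-survey items, unweighted sum (an assumption, worst case).**
- Arm A range: 4 × 1 = 4 to 4 × 5 = 20.
- Arms B and C range: 12 × 1 + 0 = 12 to 12 × 5 + 10 = 70.
- All-midpoint answers: arm A 4 × 3 = 12; arms B and C 12 × 3 + 5 = 41. The gap is 41 − 12 = 29 points with no difference in opinion.
- If the 1-5 items were averaged instead, all-midpoint answers give 3 in every arm, and this gap disappears.

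**Reading 3: only items that every arm answers.**
- Two questions: 2 to 10 in every arm. Four items: 4 to 20 in every arm. Both are comparable.
- The two promised tests still become one. With equal SDs, between-question correlation ρ, and a standardised effect d on one question only, the standardised effect on the sum is d / √(2(1 + ρ)). Over an assumed ρ of 0, 0.5 and 1 this is 0.71d, 0.58d and 0.50d.
- If both questions shift by d, the effect is 2d / √(2(1 + ρ)), or 1.15d at ρ = 0.5. Pooling can therefore help or hurt; either way it is a different outcome from the one in 3.2.

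**Illustrative simulation.** Kruskal-Wallis at 0.05, with the planned 125 patients split 42/42/41 and no true arm difference on the shared items. Assumptions not taken from the documents: answer probabilities 5/10/20/35/30% for scores 1 to 5, latent inter-item correlation 0.5, no missing data. There were 3,000 runs per row, except 300 for the all-item sum.

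| Composite | Rejection rate |
|---|---|
| Sum of the 2 primary questions | 0.050 |
| Sum of the 4 shared items | 0.049 |
| Sum of all 1-5 items (4 vs 12) | 1.00 |
| Mean of all 1-5 items, extra items answered alike | 0.052 |
| Mean of all 1-5 items, extra items answered lower (15/20/30/20/15%) | 0.79 |

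Shared-item composites hold the nominal level. Composites that include arm-specific items may or may not, depending on how those items are scored and answered.

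**The comparison.** Sections 3.1 and 3.2 specify two groups, B + C and A. Section 9 specifies three groups and repeats that at 3 months. Section 3.3 lists the comparison among all arms as exploratory, at both time points.

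**The case against.** A reader might infer that the 3-month analysis as written is not comparable across arms and would produce a spurious gap of 29 points. The documents do not support that. Section 9 neither lists the items nor speaks of a sum. Its sentence refers back to the analysis just described, which concerns the questions in 3.1, and every arm answers those. Section 3.3 gives the remaining questions their own exploratory analysis and marks the nine extra ones as belonging to arms B and C. The surrounding text thus points towards the shared questions, and a composite of those is comparable. The 29 points need four assumptions together: a raw sum, all 13 items, a 0-10 item added to 1-5 items, and no reverse scoring.

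Other points also carry weight. Appendix J is not in the supplied text, so a scoring rule there cannot be excluded and the item count rests on Sections 3.1 and 3.3. The study is described as a feasibility study, the outcome is secondary, and the composite wording does not touch the co-primaries. Changing the comparison to B + C versus A at 3 months alone would leave Section 9 using different groupings at 3 and 6 months.

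The objection removes the claim of certain non-comparability. It does not remove the contradiction. Even the most favourable reading, a composite of the two primary questions, is one test where 3.2 has two, and a scoring rule in Appendix J would not make 3.2 name a composite.

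**Conclusion.** The point holds as a contradiction between sections. Section 9 applies the 3-month analysis to a score that the supplied text does not define for this survey, while 3.2 defines the outcome as two separate questions, B + C versus A. The certain consequence is that one test takes the place of two, on a variable the analyst must construct. Under the shared-question reading, an effect confined to one question would be seen at between 0.50 and 0.71 of its standardised size, assuming equal SDs and a correlation between 0 and 1.

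Loss of comparability is conditional: it arises if the symptom composite is meant, and can arise if arm-specific items are included. The 12 against 41 contrast is a worst case, not a forecast. The mismatch between a two-group outcome and a three-group test is not confined to 3 months; it affects the 6-month primary analysis in the same way. The correction is worth making because it changes which tests are run, but the composite wording affects a secondary outcome only.

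**What to change.** In Section 9, replace the reference to a composite with: the score on each of the two primary questions at 3 months, compared between arms B + C and arm A, as in Section 3.2.

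In the same edit, make the 6-month primary analysis B + C versus A, as in Section 3.1. Kruskal-Wallis applied to two groups is the rank-sum test, so the method can stay; the Tukey step is then not needed for these comparisons. The all-arm and single-arm comparisons can remain where Section 3.3 already puts them, as exploratory.

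If a composite is wanted as well, build it only from items that all arms answer, state the items and whether they are summed or averaged, and list it as an outcome in Section 3.

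The cost is a few sentences in Section 9, with no change to data collection or sample size. The edit should be dated and made before survey answers are examined by arm; if they have already been examined, the report should say so.
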